## 12.2. Treatment Period

### Day -10 to -4:

- Physical exam, neurological exam, and KPS
- Laboratory testing including:
  - CBC with differential
  - CMP
  - Beta-HCG, if appropriate and > 24 hours post screening Beta-HCG
- Ipilimumab infusion
- Nivolumab infusion

### Day 1 (prior to surgery):

- Physical exam, neurological exam, and KPS
- Laboratory testing including:
  - CBC with differential
  - CMP
  - PT, aPTT
- Whole blood (3 x 8.5 mL yellow top tubes) for immune monitoring, collected prior to surgery
- Surgical resection

### Week 3 ( $\pm$ 1 week), surgical follow-up visit:

- Physical exam, neurological exam, and KPS
- Laboratory testing including:
  - CBC with differential
  - CMP
- Whole blood (3 x 8.5 mL yellow top tubes) for immune monitoring

### Week 4 ( $\pm$ 3 weeks):

- Whole blood (3 x 10 mL yellow top tubes) for immune monitoring
- SRS treatment (number of fractions given will be at the physician's discretion)

### **12.3. End of Treatment**

Week 7 (±1 week):

- Physical exam, neurological exam, and KPS
- Laboratory testing including:
  - CBC with differential
  - CMP
  - Thyroid panel
- Whole blood (3 x 10 mL yellow top tubes) for immune monitoring

### **12.4. Follow-up Period**

Week 13 (±2 weeks) and at standard of care visits per the treating physician's discretion for up to 18 months:

- Physical exam, neurological exam, and KPS
- Laboratory testing including:
  - CBC with differential
  - CMP
  - Thyroid panel
- MRI of the brain accompanied by any standard of care systemic staging scans. Though standard of care systemic staging scans are not dictated by this protocol, the results of such scans should be included in the eCRF.

### **12.5. End of Study**

At the end of the study period, Bristol-Myers Squibb Company will not continue to supply study drug to subjects/investigators unless the Sponsor-Investigator chooses to extend their study. The investigator is responsible to ensure that the subject receives appropriate standard of care or other appropriate treatment in the independent medical judgement of the Investigator to treat the condition under study.

The study will be considered complete once enrollment has been met, follow-up procedures outlined in Section [12.4](#) have been conducted on all subjects, and data analysis is concluded. The study may also be terminated early for any reason by the PI.

Subjects that are lost to follow-up will be documented in the patient record and in the 21 CFR Part 11 database. In the compliant database, the subject will be marked as "Patient Status Unknown," along with a corresponding explanation, if any.

### **12.6. Early Withdrawal of Subject(s)**

### **12.6.1. Criteria for Early Withdrawal**

Subjects may voluntarily withdraw from the study at any time. The PI may also withdraw a subject from the study at any time based on his/her discretion. Reasons for PI-initiated withdrawal may include, but is not limited to the following:

- If, in the investigator's medical judgment, further participation would be injurious to the subject's health or wellbeing
- Protocol deviation
- Administrative issues
- Non-compliance of the subject
- Pregnancy
- They do not receive neoadjuvant nivolumab and ipilimumab infusions

### **12.6.2. Follow-up Requirements for Early Withdrawal**

Subjects should be seen in clinic or contacted at a minimum of every 3 months until 18 months after initiating study treatment, if possible.

### **12.6.3. Replacement of Early Withdrawal(s)**

Subjects who withdraw from the study without receiving both nivolumab and ipilimumab will be considered non-evaluable; those subjects will be replaced.

## **12.7. Study Assessments**

### **12.7.1. Medical History**

Standard medical history will be obtained and documented per institutional guidelines.

### **12.7.2. Physical Exam**

Standard physical exam and neurological assessment will be conducted and documented per institutional and PRTBTC guidelines.

### **12.7.3. Radiographic Review**

Starting at week 13, an MRI of the brain will be obtained at the subsequent standard of care visits outlined in Section [12.4](#). Given that imaging following immunotherapy differs greatly from what is typically seen following chemoradiation treatment or treatment with anti-angiogenic compounds, evaluation of response using Macdonald criteria or Response Assessment in Neuro-Oncology (RANO) criteria is not appropriate in this trial. Due to differences in the nature of primary brain tumors and brain metastases, a modified version of RANO called RANO-BM will be used.

### **12.7.4. Laboratory Evaluations**

The timing of laboratory assessments that will be obtained during the course of the study is given in [Table 1](#). A list of each evaluation is below.

- CBC with differential

- CMP
- PT, aPTT
- Beta-HCG, if appropriate
- Thyroid panel

### 12.7.5. Correlative Assessments

Correlative studies will assess and compare the immune response observed within patients treated with neoadjuvant immunotherapy. Inhibition of CTLA-4 and PD-1 on T cells using monoclonal antibodies (like ipilimumab and nivolumab) results in increased T-cell proliferation [17], and could serve as a surrogate marker for therapeutic efficacy. To examine T-cell proliferation rates, Ki67 staining will be performed on PD-1+/CD8+ T cells extracted both from the peripheral blood and from resected tissue (when available). Blood will be drawn longitudinally during treatment (see [Table 1](#) in Section 12) to study how a single dose of nivolumab and ipilimumab before surgery affect T-cell proliferation over time. Assessing how Ki67 levels on peripheral-blood T cells change over time in patients receiving neoadjuvant immunotherapy will provide evidence that neoadjuvant checkpoint inhibition alters T-cell function. Additional immune profiling will be performed to understand how the immune system is responding to neoadjuvant immunotherapy compared to the control group. This immune profiling will be performed with assays including, but not limited to: RNASeq, 28 color flow cytometry, and IHC. These assays may be run on cells from peripheral blood, resected tissue (if available), and archival tissue (if available). Analysis will be performed to correlate peripheral blood immune responses to those within the tumor. An alternative protocol will be established to collect fresh tissue in solid tumor brain metastases patients who are undergoing standard of care resection and not receiving immunotherapy to compare as a control for RNA sequencing and 28 color flow panels. 28 color flow panel analysis will be performed by [name] or his designee.

## 13. SAFETY MONITORING AND REPORTING

The PI is responsible for the identification and documentation of adverse events and serious adverse events, as defined below. At each study visit, the PI or designee must assess, through non-suggestive inquiries of the subject or evaluation of study assessments, whether an AE or SAE has occurred.

### 13.1. Adverse Events

An adverse event (AE) is any untoward medical occurrence in a subject receiving study drug and which does not necessarily have a causal relationship with this treatment. For this protocol, the definition of AE also includes worsening of any pre-existing medical condition. An AE can therefore be any unfavorable and unintended or worsening sign (including an abnormal laboratory finding), symptom, or disease temporally associated with the use of nivolumab or ipilimumab, whether or not related to use of nivolumab or ipilimumab. Abnormal laboratory findings that are able to be graded via CTCAE will be collected as AEs and attribution will be reviewed by the PI.

From the time the subject signs the informed consent form until 100-days after surgery, or 100 days after ipilimumab and nivolumab infusion for patients who do not undergo surgery, all AEs must be recorded in the subject medical record and adverse events case report form.

AEs will be assessed according to the CTCAE version 5. If CTCAE grading does not exist for an AE, the severity of the AE will be graded as mild (1), moderate (2), severe (3), life-threatening (4), or fatal (5).

Attribution of AEs will be indicated as follows, with the study drug specified to be ipilimumab, nivolumab, protocol-mandated surgery, or SRS:

- Definite: The AE is clearly related to the study drug
- Probably: The AE is likely related to the study drug
- Possible: The AE may be related to the study drug
- Unlikely: The AE is doubtfully related to the study drug
- Unrelated: The AE is clearly NOT related to the study drug

For additional information on adverse event management algorithms, please see Sections [18.1](#) and [18.2](#) for nivolumab and ipilimumab, respectively.

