## 12. SCREENING AND ON-STUDY TESTS AND PROCEDURES

**Table 1: Schedule of Study Tests and Procedures**

Description	Screening	Treatment Period				
	Up to 14 days prior to surgical resection	Neoadjuvant IO	Surgery		Adjuvant SRS 	Follow-up
Week 		-1	1	3 	4	7, 13 +SOC visits
Day 		-10 to -4	1	15	22 ( $\pm$ 3 weeks)	29 + SOC visits
General Evaluations						
Informed Consent	X					
Physical Exam 	X	X	X	X		X
Neurologic Exam 	X	X	X	X		X
Performance Status 	X	X	X	X		X
Adverse Events					Continuous 	
Laboratory Evaluations						
CBC w/diff	X	X 	X	X		X
CMP	X	X 	X	X		X
Thyroid panel	X					X
PT, aPTT	X					
Pregnancy test 	X	X 				
Whole blood for correlative analysis (3x10 mL yellow top) 	X		X 	X	X 	X 
Archival tissue sample 	X					
Surgical tissue sample			X 			
Disease Evaluations						
MRI of the brain 	X					X 
Treatment						
Ipilimumab		X				
Nivolumab		X				
Surgery 			X			
SRS					X	

Number of fractions for SRS treatment will be assigned at physician's discretion

Weeks and days listed are approximate.

Post-operative visit

Clinical evaluations will include a general physical examination, complete neurologic examination, and KPS rating.

Adverse events will be continuously monitored after the first study-mandated agent is administered to the patient and reviewed monthly by the study PI. AE collection will cease 100-days after surgery, or 100 days after ipilimumab/nivolumab infusion for patients who do not undergo surgery.

Only drawn if more than 7-days (24-hours for pregnancy) post screening draw

For women of childbearing potential

Whole blood should be sent to the Substrate Services Core (SSCRS) for processing and then sent to [name] laboratory

Blood should be drawn prior to surgical resection

Blood should be drawn prior to SRS

Drawn only at the week 7 follow-up visit

A sample of archival tissue from the primary or other extracranial tumor will be requested for correlative analysis, if available.

A sample of tissue from the resected metastases will be requested for correlative analysis, if available.

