#### 13.1.2. Reporting of AEs

Any AE occurrence (spontaneously volunteered and enquired for, as well as observed AEs) during the study must be documented in the patient's medical records in accordance with the Investigator's normal clinical practice and on the

AE page of the eCRF. SAEs that occur during the study must be documented in the patient's medical record, on the AE eCRF, and on the SAE form.

The Investigator should attempt to establish a diagnosis of the event based on the signs, symptoms, and/or other clinical information. In such cases, the diagnosis should be documented as the AE (and SAE if serious) and not the individual signs/symptoms.

If an abnormal laboratory finding or other abnormal assessment meets the definition of an AE, then the AE eCRF page must be completed as appropriate. In addition, if the abnormal assessment meets the criteria for being serious, the SAE form must also be completed. A diagnosis, if known, or clinical signs or symptoms if the diagnosis is unknown, rather than the clinically significant laboratory finding or abnormal assessment, should be used to complete the AE/SAE page. If no diagnosis is known and clinical signs or symptoms are not present, then the abnormal finding should be recorded. If an SAE report is completed, pertinent laboratory data should be recorded on the SAE form, preferably with baseline values and copies of laboratory reports.

A database of all adverse events (not just those considered related to the study drug) will be maintained in a 21 CFR Part 11 compliant database. The event will be categorized by organ system, relationship to treatment, its grade of severity, and resolution. The PI and study statistician will periodically review the collective adverse events with the intention of identifying any trends or patterns in toxicity. If any such trends are identified, depending on their severity and frequency, a protocol amendment will be considered.

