#### 15.5.1.3. Adverse Events

In addition to feasibility, we will also be monitoring the study for adverse events, both before, during, and after surgery.

Aggregate summaries of adverse events will be generated periodically for study team use, for review by the Safety Oversight Committee, and for submission to ClinicalTrials.gov. Included with these summaries will be a list of all patients experiencing serious adverse events.

Two tabulations will be generated--one that includes all toxicities regardless of attribution, and another that includes only toxicities that are possibly, probably, and definitely related to treatment. For each of these tabulations, the maximum grade (according to CTCAE version 5) of each type of toxicity experienced by each patient will be summarized with frequency distributions. These tabulations will also summarize adverse events by step in the treatment regimen (e.g. neoadjuvant treatment period, surgery / SRS).

For ClinicalTrials.gov, serious adverse events and other adverse events will be summarized separately. These tabulations will reflect the number of patients who experience each type of toxicity regardless of grade or attribution.

As noted in section 15.5.1.2, if the percentage of patients with surgical delay due as a direct or indirect result of ipilimumab and/or nivolumab treatment is elevated, consideration will be given to modifying the immunotherapy treatment regimen. In addition, if the prevalence of adverse events possibly, probably, or definitely related to combination immunotherapy is higher than

anticipated based upon prior experience with this combination, consideration will also be given to modifying the immunotherapy regimen.

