Grade 2-3 Mild to moderate new symptoms	
 
Delay I-O therapy per protocol
 
Pulmonary and ID consults
 
Monitor symptoms daily, consider hospitalization
 
1.0 mg/kg/day methylprednisolone IV or oral equivalent
 
Consider bronchoscopy, lung biopsy
 
	
 
Re-image every 1-3 days
 
 
If improves:
 
 
When symptoms return to near baseline, taper steroids over at least 1 month and then resume I-O therapy per protocol and consider prophylactic antibiotics
 
 
If not improving after 2 weeks or worsening:
 
 
Treat as Grade 3-4
 

Grade 4 Severe new symptoms; New/worsening hypoxia; Life-threatening	
 
Discontinue I-O therapy per protocol
 
Hospitalize
 
Pulmonary and ID consults
 
2-4 mg/kg/day methylprednisolone IV or IV equivalent
 
Add prophylactic antibiotics for opportunistic infections
 
Consider bronchoscopy, lung biopsy
 
	
If improves to baseline:
 
 
Taper steroids over at least 6 weeks
 
 
If not improving after 48 hours or worsening:
 
 
Add additional immunosuppression
 

Patients on IV steroids may be switched to an equivalent dose of oral corticosteroids (e.g. prednisone) at start of tapering or earlier, once sustained clinical improvement is observed. Lower bioavailability of oral corticosteroids should be taken into account when switching to the equivalent dose of oral corticosteroids.

**Table 5: Hepatic Adverse Event Management Algorithm.** Rule out non-inflammatory causes. If non-inflammatory cause, treat accordingly and continue I-O therapy. Consider imaging for obstruction.

Grade of Liver Test Elevation	Management	Follow-up
Grade 1 AST or ALT > ULN to 3.0 x ULN and/or T. bili > ULN to 1.5 x ULN	
 
Continue I-O therapy per protocol
 
	
 
Continue LFT monitoring per protocol
 
 
If worsens:
 
 
Treat as Grade 2 or 3-4
 

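### Laboratory adverse events have no baseline rule at collection or in the maximum-grade tables, so stable abnormalities present before infusion may be counted as toxicities

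*Combined protocol and SAP*

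**What the plan says.** Section 13.1 contains three statements that bear on laboratory values.

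- Collection: "Abnormal laboratory findings that are able to be graded via CTCAE will be collected as AEs and attribution will be reviewed by the PI".
- Definition: "the definition of AE also includes worsening of any pre-existing medical condition", and an AE can be "any unfavorable and unintended or worsening sign (including an abnormal laboratory finding), symptom, or disease temporally associated with the use of nivolumab or ipilimumab".
- Window: "From the time the subject signs the informed consent form until 100-days after surgery". Patients who have no surgery are followed for the same length of time from infusion.

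Section 13.1.2 adds a condition: "If an abnormal laboratory finding or other abnormal assessment meets the definition of an AE, then the AE eCRF page must be completed as appropriate". It prefers a diagnosis, or signs and symptoms, to the bare laboratory result. Where there is neither, the abnormal result itself is recorded. Baseline values are mentioned only as a preference on the SAE form.

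Table 1 footnote 5 gives a different start: "Adverse events will be continuously monitored after the first study-mandated agent is administered to the patient".

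Section 15.5.1.3 plans one table of all toxicities whatever their attribution and one limited to possibly, probably or definitely related toxicities. In each, "the maximum grade (according to CTCAE version 5) of each type of toxicity experienced by each patient will be summarized with frequency distributions". The ClinicalTrials.gov summary counts patients with each event type irrespective of grade and attribution.

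**The concern.** A safety table for a single infusion should separate what patients brought into the trial from what appeared or worsened afterwards. Here the collection sentence sets no change condition, recording begins before treatment, and the tabulated statistic is a raw maximum. If staff treat the collection sentence as the working rule, a patient whose abnormal result never moves is tabulated alongside one whose result became abnormal after infusion.

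The control arm was removed in the 2021 amendment, so no concurrent group shows the background frequency. The aggregate summaries go to the Safety Oversight Committee and to ClinicalTrials.gov. Under Section 13.1.2 the PI and statistician also review collective AEs for toxicity trends that could prompt an amendment. At stake is the interpretation of those descriptive summaries.

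**Working it through.** The plan has no laboratory AE figure to reproduce, so the check is mainly textual.

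**Step 1. Can patients enter with abnormal values?** Section 11.1 admits hemoglobin from 9 g/dl, platelets from 100,000/µl and neutrophils from 1000, and sets no liver-test limit. I assume that some values permitted by these limits are abnormal and gradable. The text of CTCAE version 5 is not in the documents.

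**Step 2. Follow one stable patient through the text.** Take hemoglobin just above the 9 g/dl floor at screening and unchanged at every later draw.

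| Provision | Does the stable value count? |
|---|---|
| 13.1, collection sentence | Yes, if abnormal and gradable |
| 13.1, worsening of a pre-existing condition | Not by this route, since nothing worsened |
| 13.1, sign that is unfavorable and unintended, or worsening | Unclear: worsening is one alternative, not a requirement |
| 13.1.2, must meet the AE definition | Depends on the rows above |
| 13.1.2, diagnosis preferred | May be relabelled as anemia and still counted |
| 15.5.1.3, maximum grade | If recorded, tabulated at its grade with nothing subtracted |

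Two careful coders could therefore produce different tables from the same data. Even if worsening governs, no comparator is named. Table 1 has a screening CBC and CMP for everyone, and a repeat at the infusion visit only if more than 7 days have passed.

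**Step 3. Does the start date settle it?** No. Under Section 13.1 the screening value itself falls in the window. Under Table 1 footnote 5 it does not, but the unchanged Day 1 value does. Choosing the later start leaves the stable patient countable.

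**Step 4. Illustration of size.** The inputs are N = 20 (Section 9.1), an assumed share q of patients with a gradable entry abnormality, and an assumed independent rate t of new or worsened findings. Neither q nor t comes from the documents.

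- Any gradable finding counted: N × [1 − (1 − q)(1 − t)]
- Only new or worsened findings counted: N × t
- Difference: N × q × (1 − t)

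| q | t | Any finding | New or worsened | Difference |
|---|---|---|---|---|
| 10% | 10% | 20 × 0.19 = 3.8 | 2.0 | 1.8 |
| 10% | 30% | 20 × 0.37 = 7.4 | 6.0 | 1.4 |
| 25% | 10% | 20 × 0.325 = 6.5 | 2.0 | 4.5 |
| 25% | 30% | 20 × 0.475 = 9.5 | 6.0 | 3.5 |
| 50% | 10% | 20 × 0.55 = 11.0 | 2.0 | 9.0 |
| 50% | 30% | 20 × 0.65 = 13.0 | 6.0 | 7.0 |

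The chance that at least one of 20 patients enters with such an abnormality is 1 − 0.90^20 = 0.88 at q = 10% and 1 − 0.75^20 = 0.997 at q = 25%. The difference column assumes that every stable abnormality is recorded, which is the literal reading and so an upper bound for the given q and t.

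**The case against.** The best defence is that the paragraph should be read as a whole. An AE is an untoward occurrence in someone receiving study drug, pre-existing conditions are mentioned in terms of worsening, and Section 13.1.2 requires a laboratory finding to meet the definition before the AE page is completed. On that reading an unchanged entry value is never recorded. This has force. A reader might infer that every gradable result is certain to be counted as a toxicity, and the documents do not support that: the text concerns abnormal findings, and entry is conditional. But the defence does not close the gap. The definition offers worsening as an alternative, the sentence that deals specifically with laboratory results has no such limit, and no comparator value is given.

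A reader might also try to prove the point from the appendix, where Table 5 gives Grade 1 as "AST or ALT > ULN to 3.0 x ULN". That does not work. Those tables are management algorithms, whereas AEs are graded by CTCAE version 5. Table 11 uses 2.5 x ULN for the same grade, the Table 7 footnote cites version 4, and Table 3 requires creatinine to exceed baseline for Grade 1. The appendix therefore cannot show how a stable liver test or creatinine would be graded.

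It is also fair to say that all-cause reporting is deliberate and that the consequences are limited. Accrual suspension depends on surgical delay. The AE-based consideration of changing the regimen uses related events only, and the PI can mark a stable value unrelated. Finally, a grade-increase rule does not isolate drug effect, because ordinary fluctuation and the effects of surgery also produce grade increases. Those points limit the importance of the finding but do not supply the missing baseline rule.

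**Conclusion.** The point holds as an unreconciled rule with a missing baseline convention. Stable pre-infusion laboratory abnormalities may be counted as toxicities in the all-attribution and ClinicalTrials.gov tables. The related-only table is exposed only if such values are attributed to treatment. Surgical delay, the Ki67 fold-change and the accrual-suspension rule are untouched.

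The size is unknown. Under the assumed 10–50% entry prevalence and 10–30% new or worsened rate, the literal reading adds about 1.4 to 9.0 of 20 patients. That range reflects the assumptions and is not an estimate for this trial. It would be wrong to conclude that the safety tables will be inflated by any particular number, or that the trial's main conclusions are at risk. The change is worth making because it is cheap and because no control arm will reveal the background.

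**What to change.** 1. Reconcile the collection sentence and window in Section 13.1, the condition in Section 13.1.2 and Table 1 footnote 5, so that one rule states when a laboratory finding becomes an AE and from when AEs are recorded.
2. Define laboratory baseline as the last value before infusion.
3. In Sections 13.1 and 15.5.1.3, tabulate a laboratory abnormality as an AE only if its CTCAE version 5 grade exceeds the baseline grade. Apply this to both tabulations and to the ClinicalTrials.gov summary.
4. Show pre-infusion abnormalities in the baseline characteristics table.
5. Add a shift table of baseline grade by worst post-infusion grade for each test.

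The cost is a few sentences and some extra analysis work. Screening CBC, CMP and thyroid results are already collected, so no new tests are needed. Reported laboratory AE counts may be smaller, and the shift table keeps the full picture visible.
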